1.2.4.9 Embryo-Fetal Toxicity

Based on findings in animals, Ibrutinib can cause fetal harm when administered to a pregnant woman. Ibrutinib caused malformations in rats at exposures 14 times those reported in subjects receiving the ibrutinib dose of 560 mg per day. Reduced fetal weights were observed at lower exposures. Advise women to avoid becoming pregnant while taking Ibrutinib. If this drug is used during pregnancy or if the subject becomes pregnant while taking this drug, the subject should be apprised of the potential hazard to a fetus.

As of 6 April 2013, 71/636 subjects discontinued treatment due to an adverse event, across the monotherapy and combination therapy ibrutinib studies (excluding Study PCYC-1103-CA); 62 subjects receiving monotherapy population and 9 subjects receiving combination therapy. The most frequently reported adverse events that led to treatment discontinuations were pneumonia (13 subjects), respiratory failure (4 subjects), cardiac arrest (3 subjects) and Richter's Syndrome (3 subjects).

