5. TREATMENT PLAN

Figure 1. Treatment Schema

This is a phase IB/II study that will investigate the combination of Ibrutinib with GA101 – Obinutuzumab in previously untreated CLL subjects \geq 65 years of age or subjects < 65 years that either refuse to be treated with chemotherapy or that are not candidates for treatment with chemotherapy agents.

Treatment will be given up to 6 cycles, each cycle will have duration of 28 days (Figure 1 - Appendix 2).

Ibrutinib will be given at 420 mg po daily during the complete study period (6 cycles) and will continue during the following 3 years until unacceptable toxicity

Ibrutinib + GA101 – Obinutuzumab. University of California, San Diego

or CLL progression in those subjects who respond to treatment. The first dose will be delivered in the clinic on Day 1, one to three hours before the GA101 – Obinutuzumab infusion, after which the subsequent dosing will be on an outpatient basis.

GA101- Obinutuzumab will be given at 1,000 mg / dose. The first dose given on cycle 1 will be split in 2 doses - Day 1 dose of 100mg and Day 2 dose of 900 mg. Subsequent doses of GA101 - Obinutuzumab (1,000 mg) will be administered on Cycle 1 - Days 8, 15; and on Day 1 of Cycles 2-6 (study days 29, 57, 85, 113, 141).

This research study protocol allows the subject to receive up to 8 infusions of GA101- Obinutuzumab. Even if the treatment is shown to be of benefit, additional infusions of GA101- Obinutuzumab beyond that allowed in the protocol cannot be given to the subject while they are participating in this study.

6. STUDY MEDICATIONS

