6.1 IBRUTINIB

6.1.1 Formulation

Ibrutinib will be supplied as hard gelatin 140-mg capsules for oral (PO) administration. **Pharmacyclics** will provide Ibrutinib during the complete study period (6 cycles) and after cycle 6, during the following 3 years.

6.1.2 Dosage and Administration

Ibrutinib 420 mg (3 x 140-mg capsules) is administered orally once daily with 8 ounces (approximately 240 mL) of water. The capsules should be swallowed intact and subjects should not attempt to open capsules or dissolve them in water. Each dose of Ibrutinib should be taken approximately at the same time each day. The use of CYP3A4/5 inhibitors/inducers, CYP2D6 inhibitors, and grapefruit and Seville oranges (due to CYP3A4/5 inhibition) should be avoided for the duration of the study (appendix 5).

If a dose is missed, it can be taken up to 6 hours after the scheduled time with a return to the normal schedule the following day. If the dose is more than 6 hours late, the dose should not be taken and the subjects should take the next dose at the scheduled time the next day. Missed doses should be recorded by the subjects in the drug diary.

The first dose will be delivered in the clinic on Day 1, one to three hours before the GA101 – Obinutuzumab infusion, after which subsequent dosing is typically on an outpatient basis. Ibrutinib will be dispensed to subjects in bottles at each visit. Unused Ibrutinib dispensed during previous visits must be returned to the site and drug

Ibrutinib + GA101 – Obinutuzumab. University of California, San Diego

accountability records updated at each visit. Returned capsules must not be redispensed to anyone.

After cycle 6, Ibrutinib will be administrated during the following 3 years until unacceptable toxicity or CLL progression and will be dispensed in bottles every 3 or 6 months at each follow-up visit.

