9.2 EVALUATIONS DURING STUDY TREATMENT & FOLLOW UP

- Physical examination including vital signs, performance status, lymph node, spleen, and liver measurements, adverse event assessment, concurrent medications, and transfusion requirements will be recorded prior to each new cycle.
- CBC with differential, platelets, complete metabolic panel with uric acid, LDH, albumin, creatinine, BUN, total protein, calcium, sodium, potassium, chloride, phosphorus and HCO3 will be performed during the following dates of treatment and follow up.
 - Cycle 1 Day 1,2,4
 - Cycle 1 Day 8, 15, 22
 - Cycle 2 to 5- Day 1, 8, 15, 22
 - Cycle 6 Day 1, 8, 15, 22, 28
 - Two months after completion of therapy Response assessment evaluation.
 - After response assessment every 3 months for 9 months.
 - Every 6 months until initiation of new treatment for CLL, consent withdrawal or death.
- All subjects will return to the clinic on day 4 of cycle #1 for laboratory assessment in order to evaluate the risk for TLS. Those subjects with laboratory evidence of TLS will return to the clinic on the day 4 of the subsequent cycles to continue follow-up of laboratory parameters.
- Absolute T cell count including CD3+, CD4+, and CD8+ populations will be performed on the following dates:
 - At screening or on day 1 of Cycle 1.

Ibrutinib + GA101 – Obinutuzumab. University of California, San Diego

- Two months after completion of therapy Response assessment evaluation.
- End of study
- Pregnancy monitoring for women of child bearing potential before each dose of GA101 Obinutuzumab (not required more than once monthly).

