9.4 EVALUATIONS EVERY 3 MONTHS FOR NINE MONTHS AFTER RESPONSE ASSESSMENT

After the response assessment (at 2 months after completion of study treatment), the initial follow-up evaluations will be made every 3 months during 9 months. These evaluations will include the following:

- Physical examination including vital signs, lymph node, spleen and liver measurements, performance status, adverse event assessment, current medications, and recording of transfusion of blood products.
 - Liver chemistries: (ALT, AST, total bilirubin and Alkaline phosphatase)
- CBC with differential, platelet count, complete metabolic panel with uric acid, LDH, albumin, creatinine, BUN, total protein, fasting blood glucose, calcium, sodium, potassium, chloride, phosphorus and HCO3.
- Beta-2 microglobulin, and quantitative immunoglobulin levels (IgG, IgA, IgM). Continue monitoring of quantitative immunoglobulins (IgG, IgA, and IgM) for up to 2 years after completion of therapy or until they return to baseline.
- Pregnancy monitoring for women of child bearing potential should continue with every follow-up evaluation until 12 months following the last dose of GA101 Obinutuzumab.
- Chest, abdominal and pelvic CT scan or MRI in those subjects with clinical or laboratory alterations that suggest disease progression based on IWCLL criteria.
- For subjects that maintain a CR, a MRD assessment in peripheral blood using multiparameter (4 colors) flow cytometry will be performed at 6 and 12 months in order to assess MRD.

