Visit Number				
Day of the cycle				
Visit window				
Informed Consent				
Enrollment Criteria				
Infectious disease screening ^a				
Medical and CLL history				
MD PE/VS/Ht and Wt	х	Х		х
Nurse Encounter (Infusion Center)				
Lymph node and organ examination	х	Х		х
RAI stage ^b	х	Х		х
Constitutional Symptoms	х	Х		х
ECOG Performance Status	х	Х		х
CBC/Differential/platelets	х	Х		х
Absolute T cell count ^c	х			х
PT/PTT/INR				
Comprehensive Chemistry Panel ^e	х	Х		х
Electorcardiogram ^f				
CT, MRI or PET Scan ^g	х	X ^h	Χ ⁱ	x
Adverse Events Screen	х	х		х
Concomitant Medication	х	х		х
Obinutuzumab administration (Infusion Center)				
Ibrutinib Dispensing ⁱ		х		
Bone marrow aspirate and biopsy	Xi		Χ ^m	X ⁿ
MRD assessment in prheripheral blood (Flow cytometry)		Χ°		
Quantitative inmunoglobulins ^p	х	X		х
β2-microglobulin	x	Х		х
Cytogenetics/FISH ^q	X			X
Full inmunophenotyping ^r				
Pregnancy test ^s	x	X ^t		x

CLL Prognostic Factors/Correlatives/Data Analysis ([name]'s Lab)						
Sample Collection/Processing						
ZAP-70 Flow Cytometry ^u						
VH Immunoglobulin gene mutation ^r						
Data Analysis and Statistics	Х	X		X		

Ibrutinib + GA101 – Obinutuzumab. University of California, San Diego

- a. HIV-1/2, HAAb, HBsAg, HBsAb, HBcAb (IgG, IgM), HCVAb. (If HBcAb is positive, a HBV-DNA viral load qPCR test will be performed).
- b. RAI staging system includes detailed assessment of liver, spleen, lymph nodes and hematologic laboratories (Hb, Hto and platelets).
- c. Including CD3+, CD4+, and CD8+ populations
- d. Or on day 1 of cycle 1
- e. Comprehensive Chemistry panel (CMP) that include: ALT, AST, LDH, alkaline phosphatase, total bilirubin, BUN, albumin, creatinine, uric acid, total protein, glucose, calcium, sodium, potassium, chloride, HCO3, phosphorus.
- f. As clinically indicated.
- g. Of the chest, abdomen and pelvis.
- h. CT, MRI or PET scan in those subjects with clinical or laboratory alterations that suggest disease progression based on IWCLL criteria.
- i. For subjects that maintain a CR, we will perform additional CT scans of the chest, abdomen and pelvis after 3 years of completion of study treatment in order to assess response based on clinic and radiologic parameters, and discuss the possibility of Ibrutinib discontinuation.
- j. Pills will be dispensed to subjects at each monthly visit during the 6 cycles and later, every 3 months during the follow up period. Subjects take 420 mg po daily.
- k. Within 90 days of treatment initiation.

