- I. A unilateral bone marrow biopsy and aspirate will be performed using multiparameter (4 colors) flow cytometry and histologic staining at 2 months after completion of study treatment (response assessment) in order to satisfy the IWCLL criteria.
- m. For subjects that maintain a CR, we will perform an additional bone marrow biopsy and aspirate after 3 years of completion of study treatment in order to assess MRD and discuss the possibility of Ibrutinib discontinuation.
- n. A unilateral bone marrow biopsy and aspirate will be performed to confirm CR (MRD assessment) using multiparameter (4 colors) flow cytometry and histologic staining at the end of study in subjects that meet clinical and laboratory parameters for CR in order to satisfy the IWCLL criteria.
- o. For subjects that maintain a CR, we will perform a MRD assessment in peripheral blood using multiparameter (4 colors) flow cytometry at 6 and 12 months in order to assess MRD.
- p. IgG, IgA, IgM.
- q. FISH Panel to include 11p, 13q, 17p analysis.
- r. Full immunophenotyping of blood mononuclear cells: CD3, 4, 5, 8, 19, 20.
- s. Serum βhCG monthly in women child bearing age.
- t. During 12 months after the last dose of GA101 Obinutuzumab.
- u. Performed at any time prior to therapy.

Ibrutinib + GA101 - Obinutuzumab. University of California, San Diego

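### Follow-up pregnancy testing stops 12 months after the last obinutuzumab dose (about day 506), while ibrutinib may continue in responders to about day 1,263, so about four scheduled visits on ibrutinib require no hCG test

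*Combined protocol and SAP*

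**What the plan says.** **Testing.** Sections 9.4 (3-monthly visits) and 9.5 (6-monthly visits) carry one rule: "Pregnancy monitoring for women of child bearing potential should continue with every follow-up evaluation until 12 months following the last dose of GA101 Obinutuzumab". In the Appendix 2 flowchart, the follow-up cell of the pregnancy-test row is marked with footnote t: "During 12 months after the last dose of GA101 Obinutuzumab". The label of that row carries footnote s, which calls for monthly serum hCG. During the six cycles, section 9.2 also ties testing to the antibody: "Pregnancy monitoring for women of child bearing potential before each dose of GA101 Obinutuzumab (not required more than once monthly"). Section 9.3 includes an hCG at the response assessment. Section 9.6 includes one at end of study, which it defines as new CLL treatment or withdrawal of consent. The flowchart column for three years after treatment shows no pregnancy test.

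**Exposure.** Obinutuzumab is given in cycle 1 and then "on Day 1 of Cycles 2-6 (study days 29, 57, 85, 113, 141"). Section 5 continues ibrutinib for three years after the six cycles until unacceptable toxicity "or CLL progression in those subjects who respond to treatment". Section 6.1.2 says that ibrutinib "will be dispensed in bottles every 3 or 6 months at each follow-up visit"; footnote j says "later, every 3 months during the follow up period". Section 1.2.4.9 (Embryo-Fetal Toxicity) warns: "Ibrutinib can cause fetal harm when administered to a pregnant woman".

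**The concern.** Both drugs are given together for six cycles, and then ibrutinib alone may run for three more years. The stop rule for testing is written for obinutuzumab only. A woman of childbearing potential who responds can therefore keep receiving a drug with a stated fetal risk after the last required test, at visits where she is examined and blood is drawn anyway.

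The practical stake lies in section 11.3.3. A subject who becomes pregnant on study drug must stop it at once, and that rule works only once the pregnancy is recognised. Scheduled testing is the one element of the pregnancy plan that does not depend on the subject noticing and reporting. It lapses while exposure continues.

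**Working it through.** This is calendar arithmetic.

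**Inputs**
- Cycle length 28 days, six cycles (section 5).
- Testing limit: 12 months after the last obinutuzumab dose (9.4, 9.5, footnote t).
- Ibrutinib: three years after cycle 6 (sections 5 and 6.1.2).
- Visits: response assessment 2 months after completion of study treatment (9.3), then every 3 months for 9 months (9.4), then every 6 months (9.5).
- Assumptions: completion of study treatment means the end of cycle 6; dosing is on time; one month is 30.44 days.

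**Reproducing the plan's dose days.** Day 1 of cycle c is 1 + 28 × (c − 1). For c = 2 to 6 this gives 29, 57, 85, 113 and 141, as section 5 states.

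**The gap**
- Testing ends: 141 + 365 = day 506.
- Cycle 6 ends: 6 × 28 = day 168. Ibrutinib ends at the latest: 168 + 3 × 365 = day 1,263.
- Gap: 1,263 − 506 = 757 days (757 / 365 = 2.1 years), or 757 / 1,263 = 60% of the longest planned ibrutinib period. It is shorter if ibrutinib stops early.

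**Visits**

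| Visit | Approximate day | hCG required? |
|---|---|---|
| Response assessment (9.3) | 229 | yes |
| 3-monthly (9.4) | 320, 412, 503 | yes |
| 6-monthly, on ibrutinib (9.5) | 685, 868, 1,051, 1,233 | no |

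Four visits on ibrutinib have no required test. The first 6-monthly visit already lies past the limit, so the pregnancy rule in 9.5 triggers no test on the planned schedule.

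**Sensitivity**
- I varied the month over 28, 30, 30.44 and 31 days, counted completion from day 168 or day 141, and read 12 months as 365 days or as 12 such months. The count is four throughout, with one exception: 31-day months counted from day 168 with a 365-day limit. There the third 3-monthly visit moves to day 509 and the count is five.
- The first 6-monthly visit ranges from day 617 to day 695, and the limit from day 477 to day 513. The statement about 9.5 therefore holds in every variant.
- In the base case the third 3-monthly visit (day 503) is only three days inside the limit, and the flowchart gives no window for follow-up visits. A slightly late visit would also make the count five.
- An 8-week obinutuzumab delay that also extends cycle 6 moves both ends by 56 days (to 562 and 1,319) and leaves the gap at 757 days.

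**Does footnote s close the gap?** Footnote s sits on the row label and would call for monthly tests. The follow-up cell has its own narrower footnote t, and the text of 9.4 and 9.5 agrees with t. The specific rule governs, so s does not extend testing past day 506.

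**Does the end-of-study test close it?** No. The 9.6 test follows new CLL treatment or withdrawal of consent, and a responder who completes ibrutinib may meet neither.

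**The case against.** The strongest reply is that nothing in the protocol requires hCG testing during ibrutinib alone, and that other controls cover that period.
- Effective contraception is an entry requirement (4.1 item 7, repeated in 6.4.4), and refusing it is an exclusion (4.2 item 14). The rule runs for 365 days past the last dose of study drug. Sections 6.3.1 and 6.3.3 use that term for ibrutinib, so the rule can be read to cover the whole ibrutinib period and a year beyond. The wording is ambiguous, because it also speaks of the combination and of obinutuzumab.
- Section 11.3.3 obliges a woman to inform the investigator immediately and to stop drug.
- Section 11.4.4.1 requires pregnancies up to one year after the last ibrutinib dose to be reported to the ibrutinib supplier within 24 hours of awareness.

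All of this stands, and it keeps the point small. The population limits it further: women of childbearing potential must enter by the under-65 route (chemotherapy refused or unsuitable), so few or none may enrol. Six-monthly tests can also find a pregnancy late.

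The reply does not explain the stop date. The plan chose to test as well as to require contraception while obinutuzumab matters, and 11.4.4.1 ties reporting to ibrutinib. Only scheduled detection ends with the other drug.

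A reader might also count about eight untested ibrutinib dispensings in the gap, using the 3-monthly interval in footnote j. The documents do not support resting the point on that. Section 6.1.2 places dispensing at the 3- or 6-monthly follow-up visits, and nothing establishes that between-visit dispensings are in person.

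**Conclusion.** The point holds as an optional safety improvement. The testing stop rule is tied to the drug that ends first, which leaves up to 757 days and about four scheduled visits on ibrutinib (five under one month convention) without a required hCG. This assumes on-time dosing, completion of treatment at the end of cycle 6, and a responder who takes ibrutinib for the full three years.

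Two stronger readings are tempting. One is that the protocol breaks a testing rule of its own. It does not: for ibrutinib, 1.2.4.9 asks only that women be advised to avoid pregnancy. The other is that women on ibrutinib are left unprotected. The contraception, notification and reporting provisions contradict that. The ORR analysis, the Simon design and the DLT assessment are untouched.

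**What to change.** In 9.4, 9.5 and footnote t, replace the limit with: *hCG at every scheduled follow-up visit until the later of 12 months after the last obinutuzumab dose and the end of ibrutinib, with a final hCG at the first scheduled visit after ibrutinib stops.* Add that footnote t governs footnote s during follow-up. No tests at between-visit dispensings are needed.

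The longest scheduled interval between tests on ibrutinib then becomes 6 × 30.44 = 183 days (168 to 186 with 28- to 31-day months). The closing test matters because the last visit on ibrutinib, near day 1,233, precedes the latest end of drug by about 30 days. On the 9.5 schedule it falls near day 1,233 + 183 = 1,416. Section 7 can be read as ending participation three years after the last cycle; on that reading no such visit is scheduled.

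The cost is a wording change in three places and about four to five extra assays for each affected woman: four on ibrutinib, and a fifth with the closing test. They use blood already drawn at those visits for the CBC and metabolic panel, so no visit is added.

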9.5 EVALUATION EVERY 6 MONTHS UNTIL PROGRESSION OR WITHDRAWAL FROM THE STUDY

Long-term follow-up will continue every 6 months until initiation of new treatment, consent withdrawal from the study or death, whichever occurs first. These evaluations will include the following

• Physical examination including vital signs, lymph node, spleen and liver measurements, performance status, adverse event assessment, current medications, and recording of transfusion of blood products.

Ibrutinib + GA101 - Obinutuzumab. University of California, San Diego

- Liver chemistries: (ALT, AST, total bilirubin and Alkaline phosphatase)
- CBC with differential, platelet count, complete metabolic panel with uric acid, LDH, albumin, creatinine, BUN, total protein, fasting blood glucose, calcium, sodium, potassium, chloride, phosphorus and HCO3.

Beta-2 microglobulin, quantitative immunoglobulin levels (IgG, IgA, IgM). Continue monitoring of quantitative immunoglobulins (IgG, IgA, and IgM) for up to 2 years after completion of therapy or until they return to baseline.

- Pregnancy monitoring for women of child bearing potential should continue with every follow-up evaluation until 12 months following the last dose of GA101 Obinutuzumab.
- Chest, abdominal and pelvic CT scan or MRI in those subjects with clinical or laboratory alterations that suggest disease progression based on IWCLL criteria.
- For subjects that maintain a CR (based on clinical and hematological assessments), additional CT scans of the chest, abdomen and pelvis will be performed after 3 years of completion of study treatment in order to assess response based on clinic and radiologic parameters, and discuss the possibility of Ibrutinib discontinuation.
- For subjects that maintain a CR (based on clinical and hematological assessments), an additional bone marrow biopsy and aspirate will be performed after 3 years of completion of study treatment in order to assess MRD and discuss the possibility of Ibrutinib discontinuation.

9.6 EVALUATIONS AT THE END OF STUDY

An evaluation within 30 days of the end of study will be performed. End of study is defined as initiation of new treatment for CLL or withdrawal of consent. This evaluation will include the following:

- Physical examination including vital signs, lymph node, spleen and liver measurements, performance status, adverse event assessment, concurrent medications, and recording of transfusion of blood products; AND:
 - Liver chemistries: (ALT, AST, total bilirubin and alkaline phosphatase)
- CBC with differential, platelet count, and complete metabolic panel with uric acid, LDH, albumin, creatinine, BUN, total protein, fasting blood glucose, calcium, sodium, potassium, chloride, phosphorus and HCO3.

Ibrutinib + GA101 - Obinutuzumab. University of California, San Diego

- Beta-2 microglobulin, and quantitative immunoglobulin levels (IgG, IgA, IgM).
 - Absolute T cell count including CD3+, CD4+, and CD8+ populations.
- Chest, abdominal and pelvic CT scan or MRI in order to confirm CR base don IWCLL criteria in subjects that meet clinical and laboratory parameter for CR.
- Unilateral bone marrow aspirate and biopsy will be performed to confirm CR (MRD assessment) using multiparameter (4 colors) flow cytometry and histologic staining.
 - FISH and interphase cytogenetics.
 - Serum Pregnancy Test (hCG levels) for FCBP (females of child bearing potential).

10. STATISTICAL CONSIDERATIONS AND RATIONALE

10.1 STATISTICAL MODEL

For this open-label study, descriptive statistics will be calculated for demographic and baseline characteristics, clinical response variables, immunologic variables and safety data. Each phase of this study will be analyzed separately. All tables, figures and listings will therefore be separated by study phase.

